Any Grade	Required Action: Discontinue idelalisib. Interrupt coadministered medications potentially associated with SJS/TEN. Institute treatment per institutional standards.		
Gastrointestinal Inflammation/Diarrhea			
Grade ≤1	Required Action: Obtain history of onset and duration of diarrhea, including description, number of stools, stool composition (e.g., watery, bloody, nocturnal), travel history, dietary changes and a medication review to identify possible diarrheogenic agents.		
	Required Action: Perform physical examination including assessment for fever, dizziness, abdominal pain/cramping, and weakness (e.g., evaluate for sepsis, bowel obstruction, dehydration).		
	Recommended Action: Provide anti-diarrheal (eg, loperamide) and maintain current idelalisib dose level and schedule.		
Grade 2 diarrhea or colitis (unless clinical diagnosis is established from medical history and physical examination)	Required Action: Obtain history of onset and duration of diarrhea, including description, number of stools, and stool composition (e.g., watery, bloody, nocturnal), travel history, dietary changes and a medication review to identify possible diarrheogenic agents.		
	Required Action: Perform physical examination including assessment for fever, dizziness, abdominal pain/cramping, and weakness (e.g., evaluate for sepsis, bowel obstruction, dehydration).		
	Required Action: For Grade 2 colitis or diarrhea (unless clinical diagnosis is established from medical history and physical examination), perform stool culture for routine pathogens (Salmonella, Shigella, Campylobacter species, Clostridium difficile toxin, Rotavirus, Cytomegalovirus, Adenovirus), ova and parasites (Cryptosporidium parvum, Isospora belli, Enterocytozoon bieneusi, Septata intestinalis, Strongyloides, Microsporidia, Entamoeba histolytica, Cyclospora), and Giardia antigen.		
	Recommended Action: For persistent Grade 2 colitis or diarrhea without clear etiology (clostridium difficile enterocolitis), endoscopy with biopsy ^b is strongly recommended to assess by immunohistochemistry (IHC) and PCR for CMV, Adenovirus. (Optional: If ileal biopsy is performed, consider Acid Fast Bacillus staining.)		
	Recommended Action: Provide anti-diarrheal (eg, loperamide). Consider addition of anti- inflammatory agent (eg, sulfasalazine, budesonide). Maintain current idelalisib dose level and schedule.		

	Recommendation		
NCI CTCAE Grade ^a	Idelalisib		

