Grade ≥ 3 diarrhea or colitis or persistent grade 2 diarrhea or colitis without clear etiology	Required Action: Withhold idelalisib.		
	Required Action: Obtain history of onset and duration of diarrhea, including description, number of stools, stool composition (e.g., watery, bloody, nocturnal), travel history, dietary changes and a medication review to identify possible diarrheogenic agents.		
	Required Action: Perform physical examination including assessment for fever, dizziness, abdominal pain/cramping, and weakness (e.g., evaluate for sepsis, bowel obstruction, dehydration).		
	Required Action: For Grade 3 colitis or diarrhea (unless clinical diagnosis is established from medical history and physical examination), perform stool culture for routine pathogens (Salmonella, Shigella, Campylobacter species, Clostridium difficile toxin, Rotavirus, Cytomegalovirus, Adenovirus), ova and parasites (Cryptosporidium parvum, Isospora belli, Enterocytozoon bieneusi, Septata intestinalis, Strongyloides, Microsporidia, Entamoeba histolytica, Cyclospora), and Giardia antigen.		
	Recommended Action: For Grade 3 colitis or diarrhea without clear etiology (eg, clostridium difficile enterocolitis), endoscopy with biopsy ^b isstrongly recommended to assess by immunohistochemistry (IHC) and PCR for CMV, Adenovirus (Optional: If ileal biopsy is performed, consider Acid Fast Bacillus staining.)		
	Recommended Action: At Grade ≤1, may resume idelalisib at lower dose level or discontinue at investigator discretion.		
	Recommended Action: Provide anti-diarrheal (eg, loperamide) and/or addition of anti-inflammatory agent (eg, sulfasalazine, budesonide).		
Hepatic Adverse Event	s (elevations in ALT, AST, or bilirubin)		
Grade ≤1 (ALT/AST≤3xULN) (Bilirubin≤1.5xULN)	Recommended Action: Maintain current dose level and schedule.		
Grade 2 (ALT/AST>3-5xULN) (Bilirubin>1.5- ≤3xULN)	Recommended Action: Monitor ALT, AST, ALP, and bilirubin at least 1x per week until all abnormalities are Grade ≤ 1; thereafter maintain current dose level.		
Grade 3 (ALT/AST>5-20xUL N) (Bilirubin>3-10xULN)	Recommended Action: Withhold idelalisib. Monitor ALT, AST, ALP, and bilirubin at least 1x per week until all abnormalities are Grade ≤1.		
	Recommended Action: If bilirubin abnormality was Grade <3, resume idelalisib at same dose level. If bilirubin abnormality was Grade >3, resume at lower dose level.		
	Required Action: Withhold idelalisib.		

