5.4.2.1. Investigation for Idelalisib Late Onset or Severe Diarrhea/Colitis

See CTCAE Version 4.03 for definitions of colitis and diarrhea.

Among idelalisib-treated patients who reported diarrhea or colitis, the median time to onset of any grade diarrhea or colitis was 1.9 months (range, 0.0–29.8), of grade 1 or 2 was 1.5 months (range, 0.0–15.2) and of grade 3 or 4 was 7.1 months (range, 0.5–29.8). Kaplan–Meier curves of time to onset of diarrhea or colitis are shown for all idelalisib- treated patients in Figure 5-1 {Coutre 2015}.

Figure 5-1. Kaplan-Meler Time to Diarrhea or Colitis

Idelalisib-associated severe diarrhea responds poorly to antimotility agents however, median time to resolution ranged between 1 week and 1 month across trials following interruption of idelalisib treatment and, in some instances, initiation of corticosteroid treatment {Gilead Sciences Inc 2014}.

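### Table 5-2 places unexplained persistent Grade 2 diarrhea/colitis in two rows with inconsistent dosing instructions, and the Grade 2 row does not point to the row whose instruction is mandatory

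*Protocol*

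**What the plan says.** Table 5-2 in Protocol Section 5.3.6 sets the dosing response to gastrointestinal toxicity by grade.

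- **Grade 2 row.** The label is "Grade 2 diarrhea or colitis (unless clinical diagnosis is established from medical history and physical examination" (the label's parenthesis closes there). Among its actions is a recommendation of endoscopy with biopsy "For persistent Grade 2 colitis or diarrhea without clear etiology". Its last recommended action adds an anti-diarrheal and continues: "Consider addition of anti- inflammatory agent (eg, sulfasalazine, budesonide). Maintain current idelalisib dose level and schedule".
- **Next row.** The label is "Grade ≥ 3 diarrhea or colitis or persistent grade 2 diarrhea or colitis without clear etiology". The first action is "Required Action: Withhold idelalisib". Resumption at a lower dose level once the event has settled to Grade 1 or less, or discontinuation, is a recommended action left to the investigator. Endoscopy in this row is introduced by "For Grade 3 colitis or diarrhea without clear etiology", and the required stool work-up is likewise worded for Grade 3.

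The text of Section 5.3.6 before the table ranks the two kinds of instruction: required actions are mandatory, while recommendations are guidelines from which an investigator may depart. Neither document says how long Grade 2 must last to count as persistent.

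SAP Section 7.1.7 lists diarrhea/colitis as an adverse event of interest and tabulates such events leading to dose modification, interruption and reduction.

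**The concern.** A dose-modification table works only if each event leads to one instruction. Here a subject with continuing Grade 2 diarrhea and no cause found fits both labels. One row advises an unchanged dose; the other requires a hold. A site that looks up Grade 2, finds the persistent case mentioned there, and follows the row to its end has no prompt to read further.

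Subject safety comes first: a subject might stay on drug where the protocol elsewhere makes withholding mandatory. The second stake is the meaning of the safety tables. If sites chose between the rows differently, the counts of diarrhea/colitis leading to interruption, reduction or modification would partly reflect which row was read.

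**Working it through.** No arithmetic decides this point and the plan gives no figure to reproduce, so the two rows are set side by side.

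| | Grade 2 row | Next row |
|---|---|---|
| Unexplained persistent Grade 2 named? | Yes, in the endoscopy recommendation | Yes, in the row label |
| Dosing instruction | Leave unchanged | Withhold |
| Force | Recommended | Required |
| Exception for persistent cases | None | Not needed |
| Reference to the other row | None | None |

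**Step 1: do both rows apply?** Take a subject whose Grade 2 diarrhea continues and whose history, examination and tests show no cause. The Grade 2 label is met, because no clinical diagnosis has been established. The second label is met word for word. Neither label excludes the other.

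**Step 2: does the unchanged-dose line reach this subject?** It is a separate action from the endoscopy line, and it is written for the whole row with no carve-out. On its wording, it does.

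**Step 3: does the protocol rank the two lines?** Yes. Section 5.3.6 makes the required action binding and the recommendation a guideline. A site that knows both rows apply is told by the protocol to follow the withhold line.

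**Step 4: what does the ranking leave open?** It settles the force of an action, not which row a subject is in. Entry to the second row turns on *persistent*, which has no definition, and the Grade 2 row handles the persistent case without sending the reader on. The narrative does not help. Section 5.4.2 reports that subjects with enteritis were able to continue or resume, and Section 5.4.2.1 states "Idelalisib-associated severe diarrhea responds poorly to antimotility agents", which concerns severe events. Neither says which row governs.

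**Step 5: where is each grade's work-up named?**

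| Event | Stool work-up (required) | Endoscopy (recommended) |
|---|---|---|
| Persistent Grade 2 | Grade 2 row only | Grade 2 row only |
| Grade 3 | Second row | Second row |
| Grade 4 | Neither row | Neither row |

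History and physical examination carry no grade limit in the second row, so the gap is confined to stool tests and endoscopy. For persistent Grade 2, a site must take the tests from one row and the binding dosing instruction from the other.

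**Step 6: which outputs are exposed?** The SAP Section 7.1.7 counts of events leading to interruption, reduction or modification. SAP Section 3.5.2 makes all analyses descriptive, with no formal comparison between groups. Duration of exposure (SAP Section 4.3.1) runs from first to last dose regardless of temporary interruptions, so a temporary hold does not change it.

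**Step 7: can the frequency be estimated?** Not from these documents. The available figures describe other events:

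- Grade 3 or higher diarrhea in the Phase 1 monotherapy study (Section 1.3.5.2.1): 11/191 = 5.8%. All such events fall in the second row, so their dosing instruction is not in dispute.
- Median onset of Grade 3 or 4 (Section 5.4.2.1): 7.1 months × (365.25/12)/7 = 30.9 weeks. The same remark applies.
- Median onset of Grade 1 or 2 (same section): 1.5 months × (365.25/12)/7 = 6.5 weeks, range 0.0 to 15.2 months. At the median, visits are every 2 weeks (Synopsis, first 12 weeks). This pools Grade 1 with Grade 2 and gives first onset, not the point at which an event becomes persistent.

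**The case against.** The strongest reply is that the protocol already resolves the conflict. The unchanged-dose line is a guideline, and the withhold line is mandatory and names this event in its label. The rows can also be read as a step: ordinary Grade 2 first, then persistent Grade 2. On that reading the Grade 2 row mentions persistence only to prompt endoscopy. Section 5.3.6 adds that dose adjustments should be discussed with the medical monitor where possible, which gives a second check.

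Most of this stands. A reader might infer two instructions of equal force with no rule between them; Section 5.3.6 does not support that. The reply fails on recognition. The ranking helps only a site that knows it is in the second row, and the Grade 2 row gives no signal of that. The step reading is reasonable but not written down: the first row manages the persistent case and then gives a general dosing line without exception.

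On work-up, it is fair to say that a subject with persistent Grade 2 has already met the Grade 2 row's stool-test requirement. That narrows the omission to Grade 4, together with a second row whose work-up wording does not match its label.

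**Conclusion.** The inconsistency is real and lies in the text. One event sits in two rows whose dosing lines differ. The protocol's own ranking favours the required line, but the Grade 2 row does not lead a site to it. The second row's stool and endoscopy wording covers Grade 3 only, although its label is wider.

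Stronger inferences are not supported:

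- That sites did handle the event differently. The documents show only that they could.
- That the second row fixes a restart at the lower dose level. Resumption is discretionary and discontinuation is an alternative.
- That the 5.8% rate, or the 7.1-month onset combined with wider visit spacing, measures the problem. Both concern events of Grade 3 or higher.
- That efficacy conclusions are at risk. No efficacy result depends on this wording.

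The size is therefore qualitative: a possible departure from a mandatory hold for an event whose rate is not given, and a possible effect on descriptive counts. The conclusion assumes that no definition of *persistent* and no cross-reference between the rows is given to sites elsewhere, for example in the study manual, which is not among these documents. The missing definition alone would be only a gap in detail; it matters here because the term separates two different dosing instructions.

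**What to change.** The sponsor's clinicians and safety team should reconcile the two rows so that unexplained persistent Grade 2 diarrhea/colitis sits in one row with one dosing instruction. If both mentions are kept, the Grade 2 row's dosing line needs an explicit exception and a cross-reference. If *persistent* still decides which row applies, its meaning should be stated. The second row's stool and endoscopy wording should be aligned with the grades in its label.

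This review takes no position on which dosing instruction is right, on what duration counts as persistent, or on which tests each grade needs.

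The cost is edits to two table rows in a protocol amendment and a letter to sites. Reconciling the dosing lines adds no procedure; aligning the work-up makes explicit what applies to grades the label already covers. The SAP needs no change.

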5.4.1. Dermatological Events

Subjects receiving idealisib with \geq Grade 3 rash have generally presented with a maculopapular rash on the trunk and extremities that is occasionally associated with fever and/or pruritus and responded to treatment with diphenhydramine and/or topical or oral corticosteroids.

For subjects who develop Grade ≥3 rash for which an underlying etiology cannot be identified (e.g., infection, co suspect drug), study drug must be interrupted.

Severe cutaneous reactions, including fatal events of Stevens-Johnson syndrome (SJS) and toxic epidermal necrolysis (TEN), have been reported in subjects receiving idelalisib. Assessment of potential causal association between idelalisib and the occurrence of SJS or TEN has been

b Refer to 5.4.2.2 for recommendations if the differentiation between small-bowel and large-bowel diarrhea is unclear

c CMV should be diagnosed using clinical or laboratory criteria per established institutional standard

confounded by the coadministration of antineoplastic agents (e.g., bendamustine, rituximab) and/or other concomitant medications known to be associated with SJS or TEN (e.g., allopurinol). If SJS or TEN is suspected, idelalisib and all coadministered medications associated with SJS or TEN should be interrupted and the subject treated accordingly.

Subjects should be monitored for the development of SJS, TEN, or other severe cutaneous reactions and idelalisib treatment should be discontinued if such events occur.

Severe, including fatal, mucocutaneous reactions can occur in patients receiving rituximab. These reactions include paraneoplastic pemphigus, Stevens-Johnson syndrome, lichenoid dermatitis, vesiculobullous dermatitis, and toxic epidermal necrolysis {Genentech Inc 2011}. The onset of these reactions has varied from 1 to 13 weeks following initiation of rituximab exposure. The safety of readministration of rituximab to patients with severe mucocutaneous reactions has not been determined; thus, for subjects experiencing a severe mucocutaneous reaction, rituximab should be discontinued.

Among patients receiving bendamustine, skin reactions have been reported in clinical trials and post-marketing safety reports {Cephalon 2012}. These events have included rash, toxic skin reactions, bullous exanthema, and purpura {Gavini 2012}. Cases of Stevens-Johnson syndrome and toxic epidermal necrolysis have been reported when bendamustine was administered concomitantly with allopurinol and other medications known to cause these syndromes. There may be an increased risk of skin toxicity in subjects receiving bendamustine together with trimethoprim-sulfamethoxazole. Because of coadministration of other agents, the precise relationship of cutaneous adverse events to bendamustine has often been uncertain. Where skin reactions to bendamustine do occur, they may be progressive and increase in severity with further treatment. Therefore, patients with skin reactions should be monitored closely. If skin reactions are severe or progressive, bendamustine should be discontinued.

5.4.2. Gastrointestinal Events

Isolated cases of gastrointestinal inflammation (eg, stomatitis, colitis, cecitis) have been noted in subjects receiving idelalisib. Rare cases of gastrointestinal perforation have occurred, generally in the setting of occult carcinoma, mesenteric embolus or diverticular disease. Idelalisib must be discontinued in subjects who experience bowel perforation.

Cholangitis manifest as hyperbilirubinemia out of proportion to serum transaminase elevations has been observed. While disease related factors, neutropenia, toxicity from prior therapies, effects of ongoing supportive care, or pre existing cholelithiasis may have initiated such events, it is possible that idelalisib played a contributory role. In such subjects, rechallenge with idelalisib has been possible and has not been associated with other severe adverse events. Subjects who have developed evidence of enteritis during idelalisib therapy have been successfully treated with antidiarrheals (eg, loperamide) and with enteric steroidal (eg, budesonide) or non steroidal (eg sulfasalazine [Azulfidine®]) anti-inflammatory agents and have been able to continue or resume idelalisib.

For study subjects who develop severe abdominal pain the possibility of a bowel obstruction or perforation should be considered. Appropriate clinical and radiographic examination should be performed and supportive care or surgical intervention should be considered. Upon recovery, rituximab may be resumed.

[figure not shown]
Among patients receiving rituximab in combination with chemotherapy, rare instances of life-threatening bowel obstruction or perforation has been observed {Ram 2009}, primarily in patients with NHL. In post-marketing reports, the mean time to documented gastrointestinal perforation was 6 (range 1–77) days from start of chemoimmunotherapy. It is hard to draw a definite conclusion regarding the role of rituximab in these cases, as the affected patients had multiple risk factors including lymphomatous involvement of the gastrointestinal tract, other gastrointestinal disorders, and/or the risk of concomitant treatments with chemoradiotherapy and corticosteroids. Very isolated instances of inflammatory bowel disease have been seen in patients receiving rituximab {Ardelean 2010}.

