A Phase 3, Double-Blind Extension Study Evaluating the Efficacy and Safety of Two Different Dose Levels of Single-Agent Idelalisib (GS-1101) as Therapy for Patients with Previously Treated Chronic Lymphocytic Leukemia

A Companion Study to Study GS-US-312-0116: A Phase 3, Randomized, Double-Blind, Placebo-Controlled Study Evaluating the Efficacy and Safety of Idelalisib (GS-1101) in Combination with Rituximab as Therapy for Patients with Previously Treated Chronic Lymphocytic Leukemia

Study Centers Planned:

Approximately 90 centers in the United States and in Europe

IND Number:

101254

EudraCT Number:

2011-006293-72

Objectives:

- To evaluate the effect of idelalisib (formerly GS-1101) on the onset, magnitude, and duration of tumor control
- To compare tumor control in subjects receiving rituximab alone in Study GS-US-312-0116 to that observed in the same subjects when receiving the standard dose of idelalisib alone in Study GS-US-312-0117
- To assess the effect of idelalisib on measures of subject well-being, including overall survival (OS), health-related quality of life (HRQL), and performance status
- To assess the effects of idelalisib on disease-associated biomarkers and to evaluate potential mechanisms of resistance to idelalisib
- To characterize exposure to idelalisib as determined by treatment administration and evaluation of idelalisib plasma concentrations over time
- To describe the safety profile observed with idelalisib
- To estimate health resource utilization associated with administration of idelalisib

[figure not shown]
Study Design:

This study is being conducted as part of an overall clinical program evaluating the efficacy and safety of idelalisib in the therapy of patients with previously treated chronic lymphocytic leukemia (CLL).

Within this program, the primary clinical trial (Study GS-US-312-0116) is a Phase 3, multicenter, 2-arm, randomized, double-blind, placebo-controlled, parallel-group study.

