- 5) Concurrent participation in another therapeutic clinical trial.
- 6) Prior or ongoing clinically significant illness, medical condition, surgical history, physical finding, electrocardiogram (ECG) finding, or laboratory abnormality that, in the investigator's opinion, could adversely affect the safety of the subject or impair the assessment of study results.

In the event Study GS-US-312-0116 is stopped early, subjects who are actively participating in Study GS-US-312-0116 will become eligible for this study, provided the following inclusion are met:

- 1) Participation in Study GS-US-312-0116 within 12 weeks of enrollment onto GS-US-312-0117.
- 2) For female subjects of childbearing potential, willingness to use a protocol-recommended method of contraception from the screening visit (Visit 1) throughout the study and for 30 days from the last dose of study drug.
- 3) For male subjects of childbearing potential having intercourse with females of childbearing potential, willingness to use a protocol-recommended method of contraception from the start of study drug (Visit 2) throughout the study and for 90 days following the last dose of study drug and to refrain from sperm donation from the start of study drug (Visit 2) throughout the study and for 90 days following the last dose of study drug.
- 4) In the judgment of the investigator, participation in the protocol offers an acceptable benefit-to-risk ratio when considering current CLL disease status, medical condition, and the potential benefits and risks of alternative treatments for CLL.

- 5) Willingness and ability to comply with scheduled visits, drug administration plan, imaging studies, laboratory tests, other study procedures, and study restrictions. *Note: Psychological, social, familial, or geographical factors that might preclude adequate study participation should be considered.*
- 6) Evidence of a personally signed informed consent indicating that the subject is aware of the neoplastic nature of the disease and has been informed of the procedures to be followed, the experimental nature of the therapy, alternatives, potential benefits, possible side effects, potential risks and discomforts, and other pertinent aspects of study participation.

Study Procedures/ Frequency:

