4.2.1. Inclusion Criteria

Subjects must meet all of the following inclusion criteria to be eligible for participation in this study:

- 1) Participation in Study GS-US-312-0116.
- 2) Occurrence of confirmed, definitive CLL progression while receiving study drug therapy (idelalisib/placebo) in Study GS-US-312-0116. Note: Definitive disease progression is CLL progression based on standard criteria and occurring for any reason (ie, increasing lymphadenopathy, organomegaly, or bone marrow involvement; decreasing platelet count, hemoglobin, or neutrophil count; or worsening of disease-related symptoms) other than lymphocytosis. Subjects must have confirmation by the sponsor working in collaboration with an independent review committee (IRC) that the disease has progressed on the clinical trial (Study GS-US-312-0116) before receiving secondary idelalisib therapy on this extension trial (Study GS-US-312-0117).
- 3) Presence of radiographically measurable lymphadenopathy (defined as the presence of ≥ 1 nodal lesion that measures ≥ 2.0 cm in the longest diameter [LD] and ≥ 1.0 cm in the longest perpendicular diameter [LPD] as assessed by CT or MRI).
- 4) Permanent cessation of Study GS-US-312-0116 treatment (rituximab and idelalisib/placebo) and no intervening or continuing therapy (including radiotherapy, chemotherapy, immunotherapy, or investigational therapy) for the treatment of CLL. *Note: Subjects may receive corticosteroids to manage CLL manifestations.*

- 5) The time from permanent cessation of Study GS-US-312-0116 treatment (rituximab and/or idelalisib/placebo) and the initiation of Study GS-US-312-0117 therapy is ≤12 weeks.

 Note: Study procedures performed as part of Study GS-US-312-0116 need not be repeated and can be used as screening procedures for Study GS-US-312-0117 if performed within 4 weeks prior to initiation of study drug therapy on Study GS-US-312-0117.
- 6) Karnofsky performance score of \geq 40.
- 7) Required baseline laboratory data (within 4 weeks prior to initiation of study treatment) as shown in the table below. Note: Confirmation should be considered for out-of-range values to determine if the abnormality is real or artifactual. Values should be obtained within the screening period and should generally be the most recent measurement obtained. Subjects with any degree of neutropenia, thrombocytopenia, or anemia due to CLL or prior therapy may enroll.

Table 4-1. Required Screening Laboratory Values

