5.2.2. Source

Both active idelalisib and placebo will be supplied free of charge by Gilead Sciences.

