5.4.9. Tumor Lysis Syndrome

Tumor lysis syndrome has not been observed with idelalisib monotherapy.

Subjects with tumor lysis syndrome should receive rapid reversal of hyperkalemia, intravenous hydration, antihyperuricemic agents, and appropriate cardiac and renal support, including dialysis as indicated. Upon recovery to baseline functioning, such subjects should continue study treatment.

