5.6.1. Anticancer or Experimental Therapies Other than Investigational Treatments

Except for corticosteroids (see Section 5.6.5), no other systemic anticancer therapies (including but not limited to chemotherapy, radiation, antibody therapy, immunotherapy, or other experimental therapies) of any kind are permitted. Subjects are not allowed to participate concurrently in any other therapeutic clinical study.

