1.3. Sample Size and Power

Planned Sample Size	Total of up to ~180 subjects (up to ~90 subjects per treatment arm)		
Power Statement	The sample size for this extension study is not based upon a formal statistical hypothesis. The upper bound of the sample size in this study is determined by the sample size of the preceding primary clinical trial (Study GS-US-312-0116). Assuming a $\sim 10\%$ dropout rate during Study GS-US-312-0116 and a further $\sim 10\%$ dropout rate in the transition from the primary study to the extension study, ~ 180 subjects are expected to be enrolled into Study GS-US-312-0117.		
Actual Enrollment and Impact on Power	 Actual enrollment: 161 subjects enrolled into Study GS-US-312-0117. Impact on power: Not applicable 		

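### Protocol 5.4.2 lets sites resume rituximab after a possible bowel obstruction or perforation, although 5.6.1 allows no antibody therapy in this single-agent idelalisib study

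*Protocol*

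**What the plan says.** Section 5.4.2 (Gastrointestinal Events) has a paragraph for study subjects who develop severe abdominal pain. It asks sites to consider obstruction or perforation, to examine and image, and to consider supportive or surgical care. It then closes: "Upon recovery, rituximab may be resumed". The paragraph gives no instruction on idelalisib. The opening paragraph of the same section does: idelalisib has to be discontinued when the bowel perforates.

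Section 5.6.1 says that, apart from corticosteroids, "no other systemic anticancer therapies (including but not limited to chemotherapy, radiation, antibody therapy, immunotherapy, or other experimental therapies) of any kind are permitted".

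The study title describes single-agent idelalisib, and the arms in Section 5.1.2 give only idelalisib in this study. On supply, Section 5.2.2 reads: "Both active idelalisib and placebo will be supplied free of charge by Gilead Sciences". It does not mention rituximab. Rituximab dosing is set out in Section 2.1, for the primary study GS-US-312-0116.

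For subjects entering on progression, inclusion criterion 4 in Section 4.2.1 requires "Permanent cessation of Study GS-US-312-0116 treatment (rituximab and idelalisib/placebo) and no intervening or continuing therapy". The synopsis version of that criterion joins the two drugs with and/or. The synopsis also has a separate entry list for when the primary study is stopped: "subjects who are actively participating in Study GS-US-312-0116 will become eligible for this study, provided the following inclusion are met". That list contains no requirement that rituximab has ended.

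**The concern.** One section permits a drug that another prohibits, and the permission sits in the instructions for managing a possible surgical emergency. Two errors could follow. A site that takes the sentence literally could give rituximab, which would breach 5.6.1. A site that takes it as a slip for study drug could restart idelalisib after a perforation, against the discontinuation rule in the same section. The second is the more serious for the patient, and it is the main reason to raise a point that otherwise looks editorial.

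**Working it through.** No arithmetic applies. The check is a comparison of the relevant texts.

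1. **Is the sentence an instruction or background?** It closes a paragraph addressed to study subjects, in the part of the protocol that tells sites how to evaluate and manage specific events. The published experience with rituximab and bowel events is in a separate paragraph that follows. The sentence is operational.

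2. **Does 5.6.1 cover rituximab?** Yes. Antibody therapy is named and the only exception is corticosteroids. The heading of 5.6.1 sets aside investigational treatments, but under Section 5.1.2 rituximab is not a treatment of GS-US-312-0117. No exception is made for rituximab carried over from the primary study.

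3. **Does anything reconcile the two?** Nothing found does. The visit tables in Section 6.2 (Tables 6-1 to 6-16) contain no rituximab administration. Section 5.4.3 refers to hepatitis B testing during anti-CD20 therapy, but gives no regimen and no exemption from 5.6.1.

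4. **What should happen to idelalisib in these situations, and what would a simple change of drug name do?**

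| Situation | Existing idelalisib rule | Effect of writing idelalisib in place of rituximab |
|---|---|---|
| Bowel perforation | Discontinue (5.4.2, opening paragraph) | Would allow resumption; contradicts the rule |
| Other nonhematological event, Grade ≥3, such as obstruction without perforation | Table 5-2 recommends withholding to Grade ≤1, then resuming at the initial or a lower dose, or stopping | Broadly compatible, but without the Grade ≤1 condition |
| Colitis, Grade ≥3 | Table 5-2 requires withholding; at Grade ≤1 it recommends a lower dose or stopping | Would omit the dose reduction |

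The idelalisib rules already exist. Only the pointer to them is absent from this paragraph.

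5. **Does the sentence reach the analysis?** PFS and DOR are censored when other antitumor treatment starts (Protocol 9.3.2.4; SAP 6.1.2.1 and 6.1.2.5). Long-term follow-up is requested of all subjects who withdraw (Protocol 6.2.17). No endpoint definition or result depends on the sentence.

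**The case against.** The strongest reply is that this is an editorial slip with almost no practical reach. The sentence says resumed, which presupposes rituximab in progress, and subjects entering on progression have permanently stopped it. No visit schedules it. Idelalisib handling is covered by the perforation rule and by Table 5-2, so no rule is missing. The next paragraph concerns bowel events in patients receiving rituximab, so leftover text is the simplest explanation. Most of this stands, and it sets the size of the point. It does not remove the literal conflict with 5.6.1, and the transfer entry list has no cessation criterion that would make the sentence inoperative for every subject.

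It can also be said that Sections 5.4.1 and 5.4.3 contain other text on rituximab, bendamustine and anti-CD20 therapy. Those instructions tell sites to stop or interrupt such drugs, so they do not conflict with 5.6.1 and need no change on this account.

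A reader might go further and infer that the sentence has displaced an idelalisib resumption rule. Section 5.4.9 invites the comparison, since its recovery sentence for tumor lysis syndrome refers to study treatment: "Upon recovery to baseline functioning, such subjects should continue study treatment". One parallel for a different event does not establish this. An unqualified rule allowing idelalisib to resume here would contradict the perforation rule in 5.4.2.

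**Conclusion.** The concern holds as an internal inconsistency between Protocol 5.4.2 and 5.6.1, and with the single-agent design. Severity is minor. Few if any subjects are likely to be affected: progression entrants have stopped rituximab and the visit tables do not include it. No number can be given, because the documents do not record the rituximab status of subjects who transferred when the primary study stopped. That silence is not evidence in either direction.

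The conclusion assumes that rituximab counts as antibody therapy under 5.6.1 and that no document outside the protocol and SAP overrides the sentence.

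Three stronger readings are not supported:
- **That transferred subjects were meant to continue rituximab here.** The entry list omits a cessation criterion, but 5.6.1 makes no exception for them and no dosing provision exists.
- **That resuming rituximab would end study participation under 5.9.** That section refers to initiation of additional therapy, so its application to a resumed drug is arguable.
- **That rituximab would raise bowel risk.** Section 5.4.2 itself says its role in the reported cases is hard to determine.

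**What to change.** In Protocol 5.4.2, delete the sentence permitting rituximab and replace it with a pointer to rules already in force:

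*Idelalisib must be discontinued for bowel perforation; otherwise manage idelalisib per Table 5-2 (Other Nonhematological Adverse Events row, or the diarrhea/colitis rows if colitis is the cause).*

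Do not simply change the drug name to idelalisib. Deletion alone would remove the conflict; the pointer also tells a site reading this paragraph what to do with the study drug.

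The cost is one sentence in the next amendment, with no new rule, visit, procedure or analysis.
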